6.3. Exploratory Objectives

- to investigate biomarkers and correlate these markers to clinical outcome
- to assess immune-related (ir)ORR, irDCR, irDOR, and irPFS by adapted RECIST 1.1 (immune-related RECIST [irRECIST])

7. Study Population

Individuals who do not meet the criteria for participation in this study (screen failure) may be re-screened. Individuals may be re-screened once. At the time of re-screening, the individual must sign a new informed consent form (ICF) and will be assigned a new identification number.

Central laboratory testing is required for assessment of eligibility. Note that repeating laboratory tests during the 21-day screening period does not constitute rescreening. Laboratory tests may not be repeated more than once in order to meet eligibility.

Prospective approval of protocol deviations to recruitment and enrollment criteria (also known as protocol waivers or exemptions) is not permitted.

7.1. Inclusion Criteria

Patients are eligible to be included in the study only if they meet **all** of the following criteria:

- [1] The patient has histologically or cytologically confirmed NSCLC.
 - Part A: NSCLC Stage IV (any histological type)
 - Part B: NSCLC Stage IV (squamous and nonsquamous)
 - Part C: NSCLC Stage IV in Japanese patients (squamous and nonsquamous)
 -
- [2] The patient has Stage IV NSCLC (American Joint Committee on Cancer Staging Manual, [AJCC] 7th Edition [Edge et al. 2010]) at the time of study entry.
- [3] The patient has measurable disease at the time of study entry as defined by RECIST 1.1 (Eisenhauer et al. 2009). Tumor lesions situated in a previously irradiated area are considered measurable if progression has been demonstrated in such lesions.
- [4] The patient must have progressed after 1 platinum-based chemotherapy regimen for Stage IV NSCLC. Prior therapy with VEGF/VEGFR targeting agents is permitted. Prior neoadjuvant/adjuvant therapy is permitted. Prior treatment with EGFR-TKI and ALK inhibitors is mandatory in patients with NSCLC whose tumor has EGFR-activating mutations or ALK translocations, respectively.
- [5] The patient has an evaluable tumor tissue, an archived formaldehyde fixed-paraffin embedded (FFPE) block or at a minimum 15 slides (freshly cut slides should be submitted to the central laboratory), is available for biomarker analyses, or if not available, patient is willing to undergo a tumor biopsy of an extra-central nervous system (CNS) lesion (core or excisional biopsy). See Section [10.3.2](#) for further details.

- [6] The patient has given written informed consent/assent prior to any study-specific procedures. Written consent may also be provided by a legal representative.
- [7] The patient is 18 years or older if required by local law or regulations.
- [8] The patient has resolution to Grade ≤ 1 by the National Cancer Institute Common Terminology Criteria for Adverse Events (NCI-CTCAE) Version 4.0, of all clinically significant toxic effects of prior chemotherapy, surgery, radiotherapy (with the exception of alopecia).
- [9] The patient has an Eastern Cooperative Oncology Group performance status (ECOG PS) score of 0-1 (see [Attachment 3](#)).
- [10] The patient has adequate organ function prior to treatment initiation, including:
- hematologic: absolute neutrophil count $\geq 1.5 \times 10^9/L$, platelets $\geq 100 \times 10^9/L$, and hemoglobin ≥ 9 g/dL. Transfusion of blood products (including platelets or red blood cells) or administration of colony stimulating factors (including G-CSF, GM-CSF or recombinant erythropoietin) within 4 weeks prior to study Day 1 Cycle 1 are not allowed.
 - hepatic: bilirubin $\leq 1.5 \times$ the upper limit of normal (ULN), alkaline phosphatase, alanine aminotransferase (ALT), and aspartate transaminase (AST) ≤ 3.0 times ULN. For patients with hepatic metastases, ALT and AST equaling ≤ 5.0 times ULN are acceptable.
 - renal: serum creatinine $\leq 1.2 \times$ ULN or calculated creatinine clearance (CrCl) > 50 mL/min (per the Cockcroft-Gault formula as defined in [Attachment 4](#)) for patients with creatinine levels > 1.2 institutional ULN
 - Serum albumin level > 25 g/L
 - Coagulation parameters: international normalized ratio (INR) ≤ 1.5 , or prothrombin time (PT), partial thromboplastin time (PTT), or activated partial thromboplastin time (aPTT) ≤ 5 seconds above ULN unless patient is receiving anticoagulant therapy as long as INR, PT, PTT, or aPTT is within therapeutic range of intended use of anticoagulants
- [11] The patient is a man who is sterile (including vasectomy confirmed by post-vasectomy semen analysis) or abstains from heterosexual activity or agrees to use an adequate method of contraception and to not donate sperm starting with the first dose of study therapy, during the study and for at least 6 months following the last dose of study therapy or country requirements, whichever is longer; OR

- [12] The patient is a woman of child-bearing potential who tests negative for pregnancy within 72 hours prior to receiving first dose of study medication based on a serum pregnancy test and agrees to use 2 methods of birth control or abstain from heterosexual activity during the study and for 6 months following the last dose of the study drug(s) or country requirements, whichever is longer; or be of non-child bearing potential. Non-childbearing potential is defined as (by other than medical reasons):
- ≥ 45 years of age and has not had menses for greater than 2 years,
 - amenorrheic for < 2 years without a hysterectomy and oophorectomy and a follicle-stimulating hormone value in the postmenopausal range upon pretrial (screening) evaluation, or
 - post hysterectomy, oophorectomy or tubal ligation. Documented hysterectomy or oophorectomy must be confirmed with medical records of the actual procedure or confirmed by an ultrasound. Tubal ligation must be confirmed with medical records of the actual procedure otherwise the patient must be willing to use 2 adequate barrier methods throughout the study, starting with the screening visit through 6 months after the last dose of study therapy.
- [13] The patient has an estimated life expectancy of at least 12 weeks.

7.2. Exclusion Criteria

Patients will be excluded from the study if they meet **any** of the following criteria:

- [14] The patient is currently enrolled in a clinical trial involving an investigational product (IP; hereon referred to as study treatment) or non-approved use of a drug or device (other than the study treatment/device used in this study), or concurrently enrolled in any other type of medical research judged not to be scientifically or medically compatible with this study.
- [15] Has had a prior anti-cancer mAb within 4 weeks prior to study Day 1 or who has not recovered (i.e., \leq Grade 1 or at baseline) from AEs due to agents administered more than 4 weeks earlier. Note: Subjects with \leq Grade 2 neuropathy or \leq Grade 2 alopecia are an exception to this criterion and may qualify for the study. Prior therapy with an anti-PD-1, anti-PD-L1, or anti-PD-L2 agent is not allowed.
- [16] The patient has a diagnosis of immunodeficiency or is receiving systemic steroid therapy or any other form of immunosuppressive therapy within 7 days prior to the first dose of trial treatment. The use of physiologic doses of corticosteroids may be approved after consultation with the sponsor.
- [17] The patient has undergone major surgery in the 30 days prior to study enrollment or, if earlier, they have not recovered adequately from the toxicity and/or complications from the intervention prior to starting therapy.

- [18] The patient has undergone chest irradiation within 2 weeks prior to Day 1 Cycle 1 study drugs administration, has not recovered from all radiation-related toxicities, requires corticosteroids, or has had radiation pneumonitis. A 2-week washout is required for focal palliative radiation to non-CNS disease.
- [19] The patient has brain metastases that are symptomatic. The patients who have completed radiotherapy for brain metastases at least 4 weeks prior to receiving treatment, who are now non symptomatic and are not using steroids or anticonvulsants for at least 7 days prior to receiving treatment, are eligible. Patients with asymptomatic brain metastases without need for treatment with steroids and who have not been treated with radiotherapy are eligible. This exception does not include carcinomatous meningitis which is excluded regardless of clinical stability.
- [20] The patient has a history of arterial thromboembolic event (ATE) or venous thromboembolic event (VTE) within 3 months prior to study enrollment. Patients with history of VTE beyond 3 months prior to study enrollment can be enrolled if they are appropriately treated with anticoagulation therapy according to the local standard.
- [21] The patient has a history or evidence of clinically-relevant coronary artery disease of current \geq Class III as defined by Canadian Cardiovascular Society Angina Grading Scale (Campeau 1976) or congestive heart failure of current \geq Class III as defined by the New York Heart Association.
- [22] The patient has experienced myocardial infarction within 6 months prior to study enrollment.
- [23] The patient has active infection requiring systemic therapy, including active tuberculosis or known history of infection with the human immunodeficiency virus (HIV 1/2 antibodies), or hepatitis B (e.g., HBsAg reactive) and/or C virus (e.g., HCV RNA [qualitative] is detected).
- [24] The patient has a history of significant neurological or psychiatric disorders, including dementia, seizures, or bipolar disorder, potentially precluding protocol compliance.
- [25] The patient has a history of any of the following conditions: presyncope or syncope of either unexplained or cardiovascular etiology, ventricular arrhythmia (including but not limited to ventricular tachycardia and ventricular fibrillation), or sudden cardiac arrest.
- [26] The patient has any other serious uncontrolled medical disorders or psychological conditions that would, in the opinion of the investigator, limit the patient's ability to complete the study or sign an informed consent document.

- [27] The patient has a known allergy / history of hypersensitivity reaction to any of the treatment components, including any ingredient used in the formulation of necitumumab or pembrolizumab, or any other contraindication to one of the administered treatments.
- [28] The patient is pregnant or breastfeeding, or expecting to conceive or father children within the projected duration of the trial, starting with the screening visit through 6 months after the last dose of trial treatment.
- [29] The patient has a known history of drug abuse that, in the opinion of the investigator, may have an impact on the safety of the patient and/or limit the patient's ability to complete the study or adhere to any protocol procedure.
- [30] The patient has a concurrent active malignancy and is receiving concurrent treatment with other anticancer therapy, including other chemotherapy, immunotherapy, hormonal therapy, chemo-embolization, targeted therapy, or an investigational agent. Previous history of malignancy other than NSCLC is permitted, provided that he/she has been free of disease for ≥ 3 years, with the exception of adequately treated basal or squamous cell carcinoma of the skin, preinvasive carcinoma of the cervix, in situ carcinoma of the breast, or low-grade prostate cancer with no plan for treatment intervention.
- [31] The patient has a history of an interstitial lung disease (ILD) or (non-infectious) pneumonitis that required steroids or current pneumonitis.
- [32] The patient has an active autoimmune disease or a documented history of autoimmune disease, or a syndrome that requires systemic steroids or immunosuppressive agents. Patients with vitiligo or resolved childhood asthma/atopy would be an exception to this rule. Patients that require intermittent use of bronchodilators or local steroid injections would not be excluded from the study. Replacement therapy (e.g., thyroxine, insulin, or physiologic corticosteroid replacement therapy for adrenal or pituitary insufficiency, etc.) is not considered a form of systemic treatment.
- [33] The patient has received a live vaccine within 30 days prior to the first dose of trial treatment. Examples of live vaccines include, but are not limited to, the following: measles, mumps, rubella, chicken pox, yellow fever, seasonal flu, H1N1 flu, rabies, Bacillus Calmette-Guérin (BCG), and typhoid vaccine. Seasonal flu vaccines that do not contain live virus are permitted.
- [34] The patient is or has an immediate family member (for example, spouse, parent/legal guardian, sibling, or child) who is investigational site or sponsor staff directly involved with this trial, unless prospective institutional review board (IRB) approval (by chair or designee) is given allowing exception to this criterion for a specific patient.

7.2.1. Rationale for Exclusion of Certain Study Candidates

Exclusion Criteria [14] and [15] eliminate drugs that cannot be mapped to a standard drug dictionary, or for which little data are known to analyze the potential relationship of AEs or drug

interactions. Exclusion Criteria [14] through [26] and [28] through [34] ensure that previous or currently required treatments or conditions do not complicate on-study treatment and/or analysis of data. Exclusion Criterion [27] excludes patients who may be at elevated risk of toxicity based on the known safety profile of necitumumab and pembrolizumab.

7.3. Discontinuation

The reason for discontinuation and the date of discontinuation will be collected for all patients. All enrolled patients who discontinue, regardless of whether or not they received study treatment, will have procedures performed as shown in the Study Schedule ([Attachment 1](#)).

Patients who are discontinued from study treatment early will have follow-up procedures performed as shown in the Study Schedule ([Attachment 1](#)).

If a patient withdraws informed consent, he or she must not be contacted unless he or she has explicitly provided permission and consent. Lilly may continue to use previously collected medical research data prior to the withdrawal consistent with the original authorization.

7.3.1. Discontinuation of Inadvertently Enrolled Patients

The criteria for enrollment must be followed explicitly. If the investigator site identifies a patient who did not meet enrollment criteria and who was inadvertently enrolled, the sponsor must be notified. If the sponsor identifies a patient who did not meet enrollment criteria and who was inadvertently enrolled, the investigator site will be notified. A discussion must occur between the sponsor clinical research physician (CRP) and the investigator to determine whether the patient may continue in the study, with or without study drug. Inadvertently enrolled patients may be maintained in the study and on study treatment when the Lilly CRP agrees with the investigator that it is medically appropriate for that patient. The patient may not continue in the study with or without study drug if the Lilly CRP does not agree with the investigator's determination it is medically appropriate for the patient to continue. The investigator must obtain documented approval from the Lilly CRP to allow the inadvertently enrolled patient to continue in the study with or without study drug.

7.3.2. Discontinuation of Study Therapy

Patients will be discontinued from the study treatment in the following circumstances:

- Enrollment in any other clinical trial involving a study drug or enrollment in any other type of medical research judged not to be scientifically or medically compatible with this study.
- The patient, for any reason, requires treatment with another therapeutic agent that has been demonstrated to be effective for treatment of the study indication; discontinuation from study therapy occurs prior to introduction of the new agent.
- Investigator/Physician Decision
 - The investigator/physician decides that the patient should be withdrawn from the study due to an intercurrent illness or change in the patient's condition that renders the patient unsuitable for further treatment in the opinion of the investigator.

- Any study therapy-related event that is deemed life-threatening, regardless of grade, warrants discontinuation of that therapy and/or discontinuation from all therapy if appropriate in the opinion of the investigator.
- If the patient has progressive disease (PD, confirmed by irRECIST or unconfirmed but with clinically worsening/deterioration [Section 10.1.5.1 and Table JFCQ.10.1]).
- Any event(s) which would require a given study therapy to be modified by more than 2 dose reductions or to be held for more than 6 weeks following Day 1 of the most recent cycle warrants discontinuation of that therapy.
- The patient becomes pregnant during treatment.
- Patient Decision
 - The patient or patient's designee (for example, parents or legal guardian) requests to be withdrawn from the study or study treatment.
- Sponsor Decision
 - The sponsor stops the study or stops the patient's participation in the study for medical, safety, regulatory, or other reasons consistent with applicable laws, regulations, and good clinical practices (GCP).
- The patient is significantly noncompliant with study procedures and/or treatment.
- An unacceptable AE/toxicity (for example, a persistent moderate toxicity that is intolerable to the patient).
- A Grade 3 to 4 IRR, and potentially other drug-related AEs, as specified in Section 9.4.1 below.
- Patients, who experience complete response (CR), that have been treated for at least 24 weeks from Cycle 1 Day 1 with pembrolizumab and necitumumab or pembrolizumab alone and had at least 2 treatments with pembrolizumab with or without necitumumab beyond the date when the initial CR was declared can discontinue treatment.

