7.3.3. Discontinuation from the Study

Patients will be discontinued from the study in the following circumstances:

- enrollment in any other clinical trial involving an IP or enrollment in any other type of medical research judged not to be scientifically or medically compatible with this study
- the investigator decides that the patient should be discontinued from the study
- the patient, for any reason, requires treatment with another therapeutic agent that has been demonstrated to be effective for treatment of the study indication, discontinuation from the study occurs prior to introduction of the new agent
- the patient or the patient's designee requests that the patient be withdrawn from the study
- Lilly stops the study or stops the patient's participation in the study for medical, safety, regulatory, or other reasons consistent with applicable laws, regulations, and GCP

Patients who are discontinued from study participation will not be followed for PD or survival.

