9.4.1.2. Dose Adjustments and Delays

9.4.1.2.1. Pembrolizumab

9.4.1.2.1.1. Pembrolizumab Dose Modifications

Adverse events (both nonserious and serious) associated with pembrolizumab exposure may represent an immunologic etiology. These AEs may occur shortly after the first dose or several

months after the last dose of treatment. Pembrolizumab must be withheld for drug-related toxicities and severe or life-threatening AEs as per [Table JFCQ.9.2](#).

Table JFCQ.9.2. Dose Modification Guides for Pembrolizumab Drug-Related Adverse Events

Toxicity	Hold Treatment For Grade	Timing for Restarting Treatment	Treatment Discontinuation
Diarrhea/Colitis	2-3	Toxicity resolves to Grade 0-1	Toxicity does not resolve within 12 weeks of last dose or inability to reduce corticosteroid to 10 mg or less of prednisone or equivalent per day within 12 weeks.
	4	Permanently discontinue	Permanently discontinue
AST, ALT, or Increased Bilirubin	2	Toxicity resolves to Grade 0-1	Toxicity does not resolve within 12 weeks of last dose.
	3-4	Permanently discontinue (see exception below) ^a	Permanently discontinue
Type 1 diabetes mellitus (if new onset) or Hyperglycemia	T1DM or 3-4	Hold pembrolizumab for new onset Type 1 diabetes mellitus or Grade 3-4 hyperglycemia associated with evidence of beta cell failure.	Resume pembrolizumab when patients are clinically and metabolically stable.
Hypophysitis	2-4	Toxicity resolves to Grade 0-1. Therapy with pembrolizumab can be continued while endocrine replacement therapy is instituted	Toxicity does not resolve within 12 weeks of last dose or inability to reduce corticosteroid to 10 mg or less of prednisone or equivalent per day within 12 weeks.
Hyperthyroidism	3	Toxicity resolves to Grade 0-1	Toxicity does not resolve within 12 weeks of last dose or inability to reduce corticosteroid to 10 mg or less of prednisone or equivalent per day within 12 weeks.
	4	Permanently discontinue	Permanently discontinue
Hypothyroidism		Therapy with pembrolizumab can be continued while thyroid replacement therapy is instituted	Therapy with pembrolizumab can be continued while thyroid replacement therapy is instituted.
Infusion Reaction	2 ^b	Toxicity resolves to Grade 0-1	Permanently discontinue if toxicity develops despite adequate premedication
	3-4	Permanently discontinue	Permanently discontinue

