Pneumonitis	2	Toxicity resolves to Grade 0-1	Toxicity does not resolve within 12 weeks of last dose or inability to reduce corticosteroid to 10 mg or less of prednisone or equivalent per day within 12 weeks.
	3-4	Permanently discontinue	Permanently discontinue
Renal Failure or Nephritis	2	Toxicity resolves to Grade 0-1	Toxicity does not resolve within 12 weeks of last dose or inability to reduce corticosteroid to 10 mg or less of prednisone or equivalent per day within 12 weeks.
	3-4	Permanently discontinue	Permanently discontinue
All Other Drug-Related Toxicity ^c	3	Toxicity resolves to Grade 0-1	Toxicity does not resolve within 12 weeks of last dose or inability to reduce corticosteroid to 10 mg or less of prednisone or equivalent per day within 12 weeks.
	4	Permanently discontinue	Permanently discontinue

Abbreviations: AE = adverse event; ALT = alanine aminotransferase; AST = aspartate aminotransferase; IRR = infusion-related reaction; T1DM = type 1 diabetes mellitus.

Note: Permanently discontinue for any severe or Grade 3 (Grade 2 for pneumonitis) drug-related AE that recurs or any life-threatening event.

- a For patients with liver metastasis who begin treatment with Grade 2 AST or ALT, if AST or ALT increases by greater than or equal to 50% relative to baseline and lasts for at least 1 week, then patients should be discontinued.
- b If symptoms resolve within one hour of stopping drug infusion, the infusion may be restarted at 50% of the original infusion rate (e.g., from 100 mL/hr to 50 mL/hr). Otherwise, dosing will be held until symptoms resolve and the patient should be given premedication for the next scheduled dose. Refer to [Table JFCQ.9.5 – IRR Treatment Guidelines](#) for further management details.
- c Patients with intolerable or persistent Grade 2 drug-related AE may hold study medication at physician discretion. Permanently discontinue study drug for persistent Grade 2 adverse reactions for which treatment with study drug has been held, that do not recover to Grade 0-1 within 12 weeks of the last dose.

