9.7. Treatment Compliance

Pembrolizumab and necitumumab will be administered I.V. at the investigational site, under the direction of the investigator. As a result, a patient's compliance with study drug administration is ensured. Patients should attend scheduled clinic visits and must comply with study criteria under their control.

Patients who are significantly noncompliant will be discontinued from the study. A patient will be considered significantly noncompliant if he or she delays therapy for more than 6 weeks following Day 1 of the most recent cycle during the study.

The study medication will be administered only at the investigational sites by the authorized study personnel. As a result, treatment compliance is ensured.

Potential discontinuation of a patient due to study drug noncompliance will be discussed between the investigator and the Lilly CRP before any determination is made to discontinue the patient.

10. Efficacy, Safety Evaluations, Sample Collection and Testing, and Appropriateness of Measurements

Written informed consent must be obtained prior to any study-specific pretreatment evaluations.

Study procedures related to efficacy, safety, and sample collection and testing assessments and their timing are described in the sections below and shown in the Study Schedule ([Attachment 1](#)).

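### Pembrolizumab has two hold limits, 6 weeks in Section 7.3.2 and 12 weeks in Table JFCQ.9.2, and the noncompliance rule in Section 9.7 leaves it unclear whether a long toxicity hold could end follow-up

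*Protocol*

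**What the plan says.** **The general stopping rule (Protocol 7.3.2).** The rule opens with "Any event(s) which would require a given study therapy to be modified by more than 2 dose reductions" and gives a long hold as its second trigger: "to be held for more than 6 weeks following Day 1 of the most recent cycle warrants discontinuation of that therapy". It names neither drug and exempts neither.

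**The pembrolizumab table (Protocol 9.4.1.2.1.1, Table JFCQ.9.2).** The text introduces the table as mandatory: "Pembrolizumab must be withheld for drug-related toxicities and severe or life-threatening AEs as per" the table. For held toxicities, the usual ground for discontinuation is "Toxicity does not resolve within 12 weeks of last dose or inability to reduce corticosteroid to 10 mg or less of prednisone" (daily dose, or its equivalent). Footnote c uses the same period for persistent Grade 2 reactions "that do not recover to Grade 0-1 within 12 weeks of the last dose".

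**The compliance rule (Protocol 9.7).** A patient counts as significantly noncompliant if he or she "delays therapy for more than 6 weeks following Day 1 of the most recent cycle", and such patients are to be discontinued from the study. The same section requires the investigator and the sponsor physician to confer before anyone is discontinued on this ground.

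**The consequence (Protocol 7.3.3).** "Patients who are discontinued from study participation will not be followed for PD or survival". Patients who stop study treatment only keep their follow-up under Sections 7.3 and 10.1.2.

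The SAP sets no hold limit for either drug and does not say which protocol limit prevails.

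**The concern.** Two stopping rules apply to the same drug and give different answers, with no statement of precedence. For part of a long hold, one section tells the site to stop pembrolizumab while the table lets it wait. Sites could then handle the same immune-mediated event differently, which makes exposure and reasons for treatment discontinuation harder to interpret.

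The statistical stake lies in Section 9.7. It applies the same 6 weeks to noncompliance, has no stated exception for holds that the protocol directs, and attaches removal from the study rather than from treatment. If it were applied to a toxicity hold, Section 7.3.3 would end follow-up. PFS and DOR would then be censored at the last progression-free assessment, and OS at the last date known alive or last contact. That censoring would be caused by toxicity. If patients with severe toxicity differ in prognosis, the Kaplan-Meier assumption of independent censoring fails for them.

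**Working it through.** **1. Design figure.** The documents state no figure on hold length, so there is none to reproduce. The one design figure, 83% power for Part B (Protocol 12.1), does not use hold length. It reproduces: with 54 patients and rejection at 16 or more responders, the exact binomial gives a one-sided alpha of 0.0597 at an ORR of 20% and power of 0.834 at 35%. Rejection at 15 would give an alpha of 0.107, above 0.10.

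**2. Scope of each limit.**

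| Source | Applies to | Limit | Clock starts | Consequence |
|---|---|---|---|---|
| 7.3.2 | either study drug | 6 weeks | Day 1 of most recent cycle | stop that drug |
| 9.4.1.2.2 | necitumumab | 6 weeks | Day 1 of most recent cycle | stop necitumumab |
| Table JFCQ.9.2 | pembrolizumab | 12 weeks | last dose | stop pembrolizumab |
| 9.7 | therapy, drug not named | 6 weeks | Day 1 of most recent cycle | leave the study |

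The necitumumab rule agrees with 7.3.2, so the conflict concerns pembrolizumab alone. The 12-week limit is not one stray cell. It appears in 7 of the table's 10 toxicity rows (diarrhea/colitis, AST/ALT/bilirubin, hypophysitis, hyperthyroidism, pneumonitis, renal failure/nephritis, all other drug-related toxicity) and in footnote c. Six of those 7 rows add the steroid condition; the liver row does not.

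**3. Conflict window.** Section 9.4 starts a cycle with the pembrolizumab Day 1 dose followed by necitumumab. On that definition, Day 1 of the most recent cycle is the day of the last pembrolizumab dose, and both clocks start together.

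- 6 weeks = 6 × 7 = 42 days. More than 6 weeks begins 43 days after the dose.
- 12 weeks = 12 × 7 = 84 days. The table allows waiting through 84 days after the dose.
- Window: 84 − 43 + 1 = 42 days = 2 × 21-day cycles.

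**4. The clock itself.** Section 9.4.1.2.2.1 says that necitumumab should not be delayed for pembrolizumab toxicity. If necitumumab given alone counts as a new cycle, the 6-week clock could restart during a pembrolizumab hold. If it does not, step 3 applies. The protocol does not say which.

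**5. Route to lost follow-up.**

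- 7.3.2 alone: treatment stops and follow-up continues (7.3, 10.1.2).
- 9.7 then 7.3.3: the patient leaves the study and follow-up ends.
- The status of noncompliance is itself inconsistent. 7.3.2 lists it as a reason to stop treatment, 9.7 makes it a reason to leave the study, and 7.3.3 does not list it.
- The route is most plausible for a patient already off necitumumab and on pembrolizumab alone, which Section 9.4.1.2.2.1 permits. For that patient a pembrolizumab hold delays all study therapy.

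**6. Number affected.** This would need the distribution of hold lengths. Neither document gives one, so no count or bias can be computed.

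**The case against.** **Sites would follow the drug-specific table.** The 7.3.2 sentence pairs the hold limit with a limit of two dose reductions, and only necitumumab has reduction levels (Table JFCQ.9.3). Its 6 weeks match the necitumumab rule, and 7.3.2 points to Section 9.4.1 for other drug-related events. This makes the table the likelier guide in practice. It does not settle the matter, because the wording covers either drug and nothing says that the table prevails.

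**Follow-up is protected.** Section 7.3.2 stops only the held drug. Necitumumab normally continues during a pembrolizumab hold, so the patient still attends and is still treated. In context, 9.7 can be read as delay caused by the patient, and it requires prior discussion with the sponsor physician. All of this stands. A reader might infer that patients on long toxicity holds will be removed and lost to PFS and OS; the documents support only that they could be. What remains is the missing exception in 9.7 and its mismatch with 7.3.2 and 7.3.3.

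**The window may rarely be reached.** A reader might infer the opposite, that most steroid-treated holds pass 6 weeks, because the supportive-care sections ask for tapers of at least 4 weeks. For example, improvement on cycle Day 17 plus 28 days gives Day 45, which is 44 days after the Day 1 dose. That inference fails. The taper starts at Grade 1 or less, which is already the table's restart grade, and the steroid condition is a dose of 10 mg or less of prednisone, not a completed taper. The end of the taper is therefore not the end of the hold. Several severe events are also permanently discontinued rather than held.

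**The endpoints named are secondary** in a single-arm study that Section 8.2 describes as hypothesis-generating. True, and this limits the statistical consequence. It does not excuse a stopping rule that contradicts itself for one of the two study drugs.

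**Conclusion.** The contradiction is explicit and unresolved. On the assumption that Day 1 of the most recent cycle is the day of the last pembrolizumab dose, the two rules disagree for 42 days, from day 43 to day 84 after that dose. If necitumumab given alone restarts the cycle clock, the 6-week limit falls later for patients still receiving necitumumab. The protocol leaves this open, so the ambiguity adds to the problem and does not remove it.

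Informative censoring of PFS, DOR and OS is a conditional risk. It requires that 9.7 be applied to a hold directed by the protocol and that the discussion with the sponsor physician not prevent removal. Its size cannot be estimated from the documents. No view is taken on which hold limit is right.

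**What to change.** - Reconcile Sections 7.3.2, 7.3.3, 9.7 and Table JFCQ.9.2 so that one hold limit and one clock apply to pembrolizumab. State whether necitumumab given alone during a pembrolizumab hold starts a new cycle for that clock. The choice of limit is a clinical decision for the sponsor.
- State whether 9.7 applies to holds that the protocol directs, and whether significant noncompliance ends treatment or study participation. Make 7.3.2, 7.3.3 and 9.7 agree on this.
- State that patients who stop therapy because of a toxicity hold stay in progression and survival follow-up, as Sections 7.3 and 10.1.2 already provide for treatment discontinuation.

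The cost is a wording amendment to the protocol. It adds no patients and no new procedures, and the sample size is unchanged.
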